#### 4.2.1.2 Supportive analyses of primary endpoint

Supportive analyses will be performed for the primary endpoint as well as some variations of the primary endpoint (for sensitivity analysis purpose). All primary and supportive analyses are summarized below and in Table 3-1. The full analysis set will be used unless otherwise specified.

Table 3-1 Primary efficacy endpoint, supportive endpoints & analyses

Endpoint	Analysis method	
Aggregate ARR (confirmed relapses only) (i.e., the primary efficacy variable)	Negative binomial model (treatment as main effect, number of relapses in previous year, and baseline EDSS, baseline Gd + T1 lesion count as covariates) (region will be considered)	Primary analysis
	Negative binomial model (treatment)	Supportive analysis 1
	Negative binomial model (treatment	Supportive analysis 2

RAP Module 3	Protocol No. CFTY720D2312

	as main effect, number of relapses in previous year, and baseline EDSS, baseline Gd + T1 lesion count as covariates) (region will be considered) on the full analysis set excluding subjects from site #	
	Negative binomial model (treatment as main effect, number of relapses in previous year, and baseline EDSS, baseline Gd + T1 lesion count as covariates) (region will be considered) on the per-protocol set	Supportive analysis 3
Aggregate ARR (confirmed and unconfirmed relapses)	Negative binomial model (treatment as main effect, number of relapses in previous year, and baseline EDSS, baseline Gd + T1 lesion count as covariates) (region will be considered)	Supportive analysis 4
Subject-level ARR (with imputation; confirmed relapses only)	Rank ANCOVA (treatment as main effect, number of relapses in previous year, and baseline EDSS, baseline Gd + T1 lesion count as covariates) (region will be considered)	Supportive analysis 5
Aggregate ARR (confirmed relapses only and time in study truncated at 367 days)	Negative binomial model (treatment as main effect, number of relapses in previous year, and baseline EDSS, baseline Gd + T1 lesion count as covariates) (region will be considered)	Supportive analysis 6
Aggregate ARR (confirmed relapses derived by EDSS)	Negative binomial model (treatment as main effect, number of relapses in previous year, and baseline EDSS, baseline Gd + T1 lesion count as covariates) (region will be considered)	Supportive analysis 7

- 1) For the primary endpoint, a supportive analysis will be performed using a negative binomial regression model adjusted for treatment group only.
- 2) For the primary endpoint, a supportive analysis will be performed using the same negative binomial model as it is in the primary analysis but based on the full analysis set excluding all subjects from the site # . Subjects in site # were mismanaged by the primary investigator at this site.
- 3) For the primary endpoint, a supportive analysis will be performed using the same negative binomial model as it is in the primary analysis but on the per-protocol set. Relapses that start after

study drug discontinuation will be excluded and log (time on study drug in years) rather than log (time in study in years) will be used as the offset variable in the negative binomial model with log link. The number of days on study drug is calculated as (the last study drug dose date -1st study drug dose date +1) which will be used. This is an efficacy analysis of on-treatment data for subjects without major protocol deviations.

- 4) Analyses described in the primary analysis section will be repeated for the ARR counting all relapses (including both confirmed and unconfirmed relapses).
- 5) For the subject level ARR with imputation, a supportive analysis will be performed using Rank Analysis of Covariance (ANCOVA) with treatment group as main effect, number of relapses in the previous year before study enrollment, baseline EDSS, and baseline Gd + lesion count as covariates [Stokes (2000)]. An adjustment for country or region will be considered. For subjects who do not complete the treatment phase, relapses will be imputed (see Handling dropouts in ARR calculations Section). Additionally for subject-level ARR without imputation, summaries by treatment group will be presented.
- 6) Analyses described in the primary analysis sections will be repeated for the confirmed relapses but the calculation for time in study is different. For this supportive analysis the time in study is the number of days from the first study drug dose date to the study completion visit date or the last study drug dose date whichever occurs later. If more than 367 (=12\*30+7) days is obtained, then it will be cutoff to be 367 days which corresponds to 12 months plus a 7-day window. If the study completion visit date is not available, the latest study visit date will be used instead. The time in study (years) will be calculated as the number of days in study/365.25. The confirmed relapses within this time period will be counted for each subject and will be used in the ARR computation.
- 7) Analyses described in the primary analysis sections will be repeated for the confirmed relapses where confirmation is derived based on EDSS/FS scores, not on the MS Relapses CRF. For each relapse reported on the MS Relapses CRF the confirmation status is derived as the following:
  - If no EDSS is performed between start and end dates of the relapse, then the relapse is "unconfirmed";
  - If an EDSS is performed between start and end dates of the relapse, then compare the EDSS/FS scores to the last available EDSS excluding EDSS recorded during the previous MS relapses. If there is an increase of 0.5 in EDSS or one point on two different FS or 2 points on one FS (all FS except bowel/bladder and Cerebral), the relapse is "confirmed"; otherwise it is "unconfirmed".

#### 4.2.1.3 Handling dropouts in ARR calculations

1) Negative binomial regression model for aggregate ARR on the full analysis set: For subjects who discontinue the study prematurely, the number of relapses recorded in the study will be used irrespective of whether the subject is on or off study drug and no imputation will be applied.

- 2) Negative binomial regression model for aggregate ARR on the per-protocol set: For subjects who discontinued the study drug prematurely, the number of relapses that start prior to or on the same day as the last dose date will be used and no imputation will be applied.
- 3) Rank ANCOVA model for subject-level ARR with imputation on the full analysis set:

For subjects who discontinue the study prematurely, the number of relapses per month for the months after discontinuation will be imputed by the corresponding monthly mean number of relapses of subjects across all treatment groups who has data of either 0 (no relapse) or 1 (one relapse) in that month. That is, for each month with completely missing data, the imputed number of relapses for the month is the average number of relapses for the corresponding month based on the available data from all subjects.

Subjects may have data from part of the month during which they drop out. The number of relapses for that month will be the observed number of confirmed relapse (either 0 or 1) during that partial month. That is, if a subject drops out with one relapse during the dropout month, the subject will be counted as having one relapse for the entire month. If no relapse is observed in the dropout month, the subject is assumed to have no relapse for the entire month. This is accurate because a subject could only have at most one confirmed relapse in each month due to the definition of confirmed relapse in the protocol (Appearance of a new neurological abnormality or worsening of previously stable or improving pre-existing neurological abnormality, separated by at least 30 days from onset of a preceding clinical demyelinating event).

Only the relapse start date will be used to determine the month in which a relapse will be counted when calculating the number of relapses per month.

The ARR of these subjects will be calculated based on the observed number of relapses before dropping out and the imputed number of relapses after dropping out. For example, suppose that the average number of relapses for each month based on all subjects contributing data to the month is as shown in Table 3-2.

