9.4.3 Handling of missing values, censoring, and discontinuations

All patients in the FAS will be included in the primary analysis, i.e., the number of confirmed relapses observed up to the end of patient's participation in the study. Patients who discontinue from study treatment will remain in the study and follow the assessment schedule. Relapses will be counted regardless of whether a patient is on or off study drug. Therefore, it is expected that all randomized patients can contribute to the primary analysis. The primary analysis model adjusts for missing information (early study discontinuations) under some statistical assumptions (noninformative dropouts and constant ARR).

Additionally the following supportive analyses will be conducted:

The primary analysis will be repeated using the per-protocol set to provide an analysis of ontreatment data from patients who have no major protocol violations. Relapses that occurred after permanent discontinuation of study drug will be excluded and log (time on study drug in years) rather than log (time on study in years) will be used as the offset variable in the negative binomial model with log link.

To assess the impact of missing data on the primary analysis, a sensitivity analysis will be performed on ARRs in the full-analysis set using a nonparametric method with imputations. The ARRs will be analyzed by means of a rank analysis of covariance (ANCOVA) with treatment, and number of relapses in the previous year before study enrollment, baseline EDSS, and baseline number of Gd-enhancing T1 lesions as covariates (Stokes 2000). An adjustment for country or region can be considered prior to database lock and will be defined in the analysis plan. A month-by-month imputation scheme will be used whereby missing data in any given month of the study will be imputed with the overall mean number of relapses (calculated from all patients across all treatment groups) in the corresponding month.

A supplementary analysis using the same negative binomial model as in the primary analysis to be performed on all relapses (i.e., confirmed and unconfirmed relapses) in the full-analysis set will be performed. Additional analyses to further assess the robustness of the results maybe prespecified in the statistical analysis plan.

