		Updated to remove 'unenhanced' in the label for T1 lesion to be consistent with source data label and also per comment (NVS).
	14MAY2018	Updated Section 3.9 Pooling of Centers by added a few more US states per the final clinical document.
		Added a complete list of centers with geographic locations and region classification in Appendix 1.
Final 2.5	22Aug2018	For PFT section, a note is added to clarify how to handle a few outliers (unrealistic values) in the final analysis.
	28Aug2018	Section 8.1.2.1 Occurrence of SAEs and NSAEs: Added the entire section to add two tables to meet the CTSD requirement.
		Section 8.1.3 Data summaries for AEs: Added two bullets for the two new tables described in Section 8.1.2.1.
	10Sep2018	Section 3.6 Study Medication: Added data handling rule for partial end date for the last dosing interval.
		Section 3.8.7 Last dose day of randomized study medication: Added data handling rule for partial or completely missing last dose date on the CMP panel.
		Section 4.1.3 Time in study (years) for aggregate ARR: Updated to use the new definition by excluding FU visits and removing the truncation at 367 days.
		Section 4.2.1.2 Supportive analysis: Moved the old definition for time in study for ARR calculation to this section and kept it as one

Version	Date	Changes
		supportive analysis.
		Section 4.2.1.2 Supportive analysis: Added additional sensitivity analysis by defining confirmed relapse strictly based on EDSS scores.
		Section 4.2.2.1 MRI: Added sensitivity analyses to exclude baseline assessments > 45 days before randomization and end of treatment assessments > 45 days after last dose.
	13Sep2018	Section 8.1 Adverse Events: Added summaries for risk AEs and updated wording for occurrence rate of AEs to be consistent with study D2311.
Final 2.6	02Nov2018	Section 4.2.2.1: Added new analyses for annualized rate of brain atrophy (ARBA) at Month 12/end of treatment. This is to adjust for study duration and also other MRI covariates due to some differences between treatment groups.

RAP Module 3

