# 3.2 Subject disposition

Subject disposition will be summarized on the randomized set. The number and proportion of subjects who complete the study or discontinue the study prematurely along with the reason for discontinuation will be presented. The number and proportion of subjects who discontinue the study drug prematurely along with the reason for study drug discontinuation will be summarized and presented separately. A listing will also be provided with treatment group and subject number.

Additionally two types of subject discontinuation listings will be provided per FDA request.

- Discontinuation of study drug after which patients are still allowed to continue to have efficacy/safety assessment according to abbreviated schedule without receiving study drug treatment until the end of study.
- Discontinuation from the study in which no further safety/efficacy will be assessed except for follow-up.

Due to the non-specific nature of the HA communication, both types of listings are provided with the additional detail requested (under the heading "Relevant information related to reason").

Reasons for screen failure will be summarized for all screened subjects.

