**Table 3-2 Example of imputation** 

Month	Average # of relapses
1	0.20
2	0.19
3	0.18
4	0.17
5	0.16
6	0.15
7	0.14

8	0.13
9	0.11
10	0.11
11	0.11

0.11

12

If a subject discontinues the study on Day 130 (i.e., after 4 months and 10 days) after having one confirmed relapse, his number of relapses from Month 6 on will be imputed from the above table. His total number of relapses will be the sum of 1, 0.15, 0.14, 0.13, 0.11...0.11, which equals to 1.86. Note that the imputed portion of the number of relapses will be the same for subjects who drop out in the same month.

The imputation will only apply to the dropout subjects up to 360 days (i.e., 12 months). After the imputation, the number of days in study for all dropout subjects is 360 days. For those who complete the study, the number of days in study will remain the same as defined in Time in study for aggregate ARR Section 4.1.3.

4) Summary of subject-level ARR without imputation on the full analysis set: For subjects who discontinue the study prematurely, the number of relapses recorded in the study will be used and no imputation will be applied.

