## 10 Determination of sample size

The study will randomize a total of 1960 patients, and is planned to provide approximately 90% power for the comparison of fingolimod 0.5 mg to glatiramer acetate at a 2-sided significance level of 0.05.

The sample size calculation is based on simulations from a negative binomial distribution with a constant dispersion parameter k.

The power of the study was evaluated under various ARR assumptions and various dropout patterns based on the cumulative literature on glatiramer acetate and the Novartis data on fingolimod. The basis of the assumptions for this study and their level of uncertainty are presented in Section 9.4.2 under the sub-header "Multiplicity adjustment for statistical hypothesis testing". The anticipated overdispersion parameter (k=0.2231) was observed in the Month-12 analysis of Study CFTY720D2301. The anticipated ARR for subjects treated with 0.5 mg fingolimod is  $\mu_{FTY~0.5~mg} = 0.195$ , the ARR for those treated with glatiramer acetate is  $\mu_{glatiramer~acetate} = 0.30$ . Therefore, the estimated ARR reduction for fingolimod 0.5 mg versus glatiramer acetate is 35%.

The total sample size of 1960 randomized is predetermined but the exact sample size of each arm will depend on when the randomization ratio switch occurs. For example, if the randomization ratio is switched when a total of 800 patients have been randomized from an original ratio of 1:1:1 for fingolimod 0.25 mg, fingolimod 0.5 mg, or glatiramer acetate, respectively to a ratio of 5:3:2, then 847 patients will be randomized to fingolimod 0.25 mg, 615 patients to fingolimod 0.5 mg and 498 patients glatiramer acetate, which will provide more than 90% power to demonstrate superiority of fingolimod 0.5 mg dose versus glatiramer acetate in terms of ARR at a 2-sided significance level of

0.05 assuming a 15% drop-out rate. The calculations take into account that patients who discontinue prematurely from the study can participate with partial data to the primary endpoint.

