## 12.1.1.2 Rank Analysis of Covariance (ANCOVA) and Rank Analysis of Variance (ANOVA)

Rank Analysis of Covariance (ANCOVA)

The supportive efficacy variable, subject-level ARR (confirmed relapse only), will be analyzed using the rank ANCOVA. Other secondary efficacy variables, subject-level ARR (confirmed and unconfirmed relapse), change from baseline in MRI variables, will be analyzed similarly on the full analysis set.

The rank ANCOVA is a non-parametric statistical method described in Stokes, Davis, and Koch (2000). It can be considered as an extension to the Wilcoxon rank-sum test with the ability to adjust for covariates in the model.

The analysis can be easily implemented using SAS by the following three steps:

- 1) compute the ranks of the response variable and covariate in the combined group of treatment using PROC RANK;
- 2) calculate the residuals from the linear regression of the response variable ranks vs. ranks of the covariates (without treatment) using PROC REG;
- 3) use the CMH mean score statistics to compare the mean values of the residuals in treatment by using TABLE scores (default scores) in PROC FREQ.

Below is an example of the SAS codes used to perform this rank ANCOVA. The independent variables and covariates in the model may change per analysis defined in this document.

\*\*\*\*\*\*\*\*\*\*\*\*\*\*\*\*\*\*\*

```
* SAS Codes: Rank ANCOVA model

* Variables in the model:

* relann = subject-level annualized relapse rates

* trt = treatment group code

* regla = region code

* n2 = number of relapses in previous year

* bledss = baseline EDSS
```

Protocol No. CFTY720D2312

```
* other covariates as well
* sid1a = subject ID
*******************
Data eff:
    Set eff;
    If regla=' ' or n2=. or bledss=. or relann=.then delete;
run;
proc rank data=eff nplus1 ties=mean out=ranks;
    by regla;
    var n2 bledss relann more convariates...;
run;
proc reg data=ranks noprint;
    by regla;
    model relann=n2 bledss more convariates...;
    output out=residual r=resid;
run;
proc freq data=residual;
    tables regla*trt*resid / noprint cmh2;
    where trt in ('A','B');
    output out=rancova cmh2;
    *** SELECT P CMHRMS;
run;
```

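### The missing-data sensitivity analysis ranks fractional imputed relapse counts, so leaving the study early scores almost like relapsing: about 10 points of power are lost at 15% dropout, and unequal dropout biases the test

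*SAP*

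**What the plan says.** Protocol 9.4.3 gives the rank analysis a specific task: "To assess the impact of missing data on the primary analysis, a sensitivity analysis will be performed on ARRs in the full-analysis set". It also fixes the rule: "missing data in any given month of the study will be imputed with the overall mean number of relapses", the mean being taken over all patients in all treatment groups.

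The SAP implements this as supportive analysis 5 of seven (4.2.1.2, Table 3-1). Under 4.2.1.3 item 3, "the number of relapses per month for the months after discontinuation will be imputed by the corresponding monthly mean number of relapses". The month of dropout keeps its observed 0 or 1, so only fully missing months are filled. "After the imputation, the number of days in study for all dropout subjects is 360 days", while completers keep their actual days. In the Table 3-2 example, a patient with one relapse who leaves on Day 130 ends with 1.86 relapses.

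The test itself is in SAP 12.1.1.2. Its first step is to "compute the ranks of the response variable and covariate in the combined group of treatment using PROC RANK"; the sample code does this within region. The ranks are then regressed on the ranked covariates, and the residuals are compared by a CMH mean score test.

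The only dropout figure is in the sample size text (SAP section 10), which gives power at a two-sided level of "0.05 assuming a 15% drop-out rate". No split by arm and no timing are given.

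**The concern.** A fractional expected count is harmless in a mean, but not in a rank. Annual relapse counts at the planned rates are mostly zero, so the lower part of the ranking is one large tied block of relapse-free completers. Adding any positive fraction to a relapse-free dropout moves that patient above the whole block, before covariate adjustment. The size of the fraction hardly matters. The test therefore responds to who left the study, even when leaving has nothing to do with relapses.

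Two things are at stake. With equal dropout, the analysis loses power through the imputation rule itself and may appear to contradict a true primary result. With unequal dropout, it favours the arm with less dropout. It is the only listed analysis that imputes missing primary-endpoint data, so the primary model's assumption of noninformative dropout would be left without a sound check.

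**Working it through.** **Inputs.** ARRs 0.195 (0.5 mg), 0.225 (0.25 mg) and 0.30 (glatiramer acetate), k = 0.2231 and 15% dropout (Protocol 9.4.2 and 9.6, SAP 10); final arms 352, 370 and 342 in the same order (SAP 10). Not in the documents and therefore assumed: dropout timing, any split by arm, and covariate and region distributions.

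**1. The plan's own figure.** No power is stated for the rank analysis, so the check uses the primary model: Var(log ratio) = 1/(n1·r1·t) + 1/(n0·r0·t) + k(1/n1 + 1/n0). With 15% uniform dropout, t = 0.925. For 352 versus 342:

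0.01575 + 0.01054 + 0.00129 = 0.02757, SE 0.1661; |ln 0.65|/SE = 0.4308/0.1661 = 2.594; power = Φ(2.594 − 1.960) = 73.7%.

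With t = 0.85 it is 70.3%. The SAP's 71% lies between, so the inputs are read correctly. At the planned 615 versus 498, t = 0.925 gives 91.0%, matching the stated figure of more than 90%.

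**2. Size of the imputed part.** In Table 3-2 it is 0.15 + 0.14 + 0.13 + 4 × 0.11 = 0.86. At ARR 0.25 the same seven months add 0.25 × 210/365.25 = 0.14. Both exceed 0, so both clear the tied block.

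**3. Where dropouts land (ARR 0.25, 15% uniform dropout).**
- Mean count over 360 days: 0.25 × 360/365.25 = 0.2464. P(no relapse) = (1 + 0.2231 × 0.2464)^(−1/0.2231) = 0.787.
- Relapse-free completers: 0.85 × 0.787 = 0.669 of all patients.
- Relapse-free dropouts: about 0.888 of dropouts, or 0.15 × 0.888 = 0.133 of all patients. About 92.5% of them have a fully missing month (0.123); the other 0.010 stay tied at 0.
- Tied block: 0.669 + 0.010 = 0.679, mean fractional rank 0.34.
- Lifted dropouts: 0.679 to 0.802, midpoint 0.74. All relapse-free dropouts: 0.925 × 0.74 + 0.075 × 0.34 = 0.71.
- Patients with a relapse: 0.802 to 1, midpoint 0.90.
- Dropout as a share of a real relapse: (0.71 − 0.34)/(0.90 − 0.34) = 0.66.

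The share lifted is about 84% if dropout is late-weighted and over 99% if early-weighted.

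**4. Simulation of the SAP steps.** Gamma-Poisson counts, twelve 30-day months, at most one relapse per month, ranks within six regions, residuals on three covariates, CMH mean score; 4,000 runs per scenario.

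| 0.195 vs 0.30, final sizes, 15% dropout in every arm | Power |
|---|---|
| Planned rank analysis | 57% |
| Same rank test on whole-count imputations | 68% |
| Primary model, observed data | 71% |
| Rank test with no dropout at all | 70% |

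The like-for-like contrast is 57% against 68%; the no-dropout row also contains genuine information loss. Early, uniform and late dropout give 56–57%. Error at equal dropout is 4.7–5.1%.

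A separate simulation compared the planned rule with ranking observed counts: 59.1% versus 69.3% at final sizes without covariates, 54.1% versus 65.3% with prognostic covariates, and 77.4% versus 87.2% at planned sizes without covariates.

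**5. Unequal dropout (assumed splits, 0.5 mg/glatiramer acetate).** Two-sided error when both arms share the same true ARR:

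| Split | ARR 0.195 | 0.25 | 0.30 |
|---|---|---|---|
| 14/16 | 6.9% | 6.4% | 5.6% |
| 13/17 | 11.3% | 8.6% | 8.7% |
| 12/18 | 18.6% | 15.2% | 12.9% |
| 10/20 | 42% | 34% | 27% |

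Power for 0.195 versus 0.30 is 78% at 13/17 and 33% at 17/13. The primary model gives 71–72% at both.

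**The case against.** The strongest case concerns weight. This is a supportive analysis with no alpha and no decision rule, the primary model imputes nothing, and the documents promise no power for the rank test. All of that stands, and it limits the consequence.

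The large error rates need an assumed split. That also stands: at the only documented figure, 15% with no split, error is nominal. The disposition tables would show an imbalance (SAP 3.2: "The number and proportion of subjects who complete the study or discontinue the study prematurely along with the reason for discontinuation will be presented"), as would the unimputed subject-level summaries. They reveal the problem but do not correct the test.

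A glatiramer-rate imputation also has lower power: 61% with the rank test and 65% with the primary model at equal dropout. This is true, but that loss follows from a stated, deliberately conservative assumption and is stable at 13/17 and 17/13 (59–61% and 63–66%). The planned rule swings from 78% to 33%.

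Simply ranking observed counts would be cheaper and recovers about 10 points at equal dropout. But it too depends on dropout: 6.9% error at 10/20, and power of 64% at 13/17 against 75% at 17/13. It also tests no missing-data assumption.

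Finally, the CMH variance is a null-hypothesis variance, so combining it by Rubin's rules rests on simulation only; the result is somewhat conservative. This favours the primary model as the main analysis of the imputed data.

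**Conclusion.** The concern holds. As written, supportive analysis 5 treats early departure as roughly two-thirds of a relapse. At the documented 15% dropout it loses about 10 points of power to the imputation rule, whatever the dropout timing. If dropout differs between arms, it is biased towards the arm with less dropout: slightly at 14/16, severely at 10/20.

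The ranking mechanism follows from the SAP text alone. The power figures rest on the planned ARRs, k = 0.2231 and assumed covariate effects; without covariates the loss against ranking observed counts is similar. The error figures rest on assumed splits. The primary negative binomial test, the testing hierarchy and the formal conclusion are not affected. It should be fixed because Protocol 9.4.3 names this analysis for judging missing data, and it cannot do that reliably.

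**What to change.** - **Replace the fractional imputation** by multiple imputation of whole relapse counts for unobserved time, from the negative binomial model. Condition each draw on the patient's own observed count and redraw the parameters, including k, each time. Prespecify the number of draws (at least 20), analyse each data set with the primary model and combine by Rubin's rules.
- **Add a departure from noninformative dropout.** Imputing at the glatiramer acetate rate is one option, with own-arm imputation as the benchmark.
- **If the rank ANCOVA is kept**, run it on the whole-count data sets with the same time denominator for dropouts and completers, combining the region-weighted difference in mean residual rank and its CMH variance.
- **Align the wording.** SAP 4.2.1.2 item 5 ties imputation to not finishing treatment, whereas 4.2.1.3 ties it to leaving the study. It should apply only to months unobserved because the patient left the study.

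Check of the fix (1,000 runs, 20 draws; Monte Carlo standard error about 1.5 points at 68%, from √(0.68 × 0.32/1000)). Error is at ARR 0.25 for 15/15, 13/17 and 10/20; power is for 15/15, 13/17 and 17/13:

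| Analysis | Error | Power |
|---|---|---|
| Planned rank | 5.0, 9.6, 33.5% | 58, 78, 33% |
| Whole-count rank, own-arm | 3.5, 4.8, 4.8% | 68, 67, 67% |
| Whole-count rank, glatiramer-rate | 2.8, 3.7, 3.8% | 61, 61, 59% |
| Whole-count primary model, own-arm | 4.2, 4.5, 4.8% | 72, 72, 71% |
| Whole-count primary model, glatiramer-rate | 3.3, 3.7, 3.5% | 65, 66, 63% |

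The cost is programming, SAP wording and a documented departure from Protocol 9.4.3; no new data are needed. The Final 2.6 entry in the SAP history explains an added MRI analysis with "This is to adjust for study duration and also other MRI covariates due to some differences between treatment groups". This suggests, but does not prove, that arm-level data had been seen. If treatment codes were already open, label the new analysis post hoc and report the planned one beside it.
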